14.3.7.2 Efficacy over time

To further explore possible early onset of effect and general efficacy over time, the following endpoints will be evaluated at each scheduled assessment up to Week 6 or each week up to Week 7:

- vIGA-AD TS at each scheduled assessment until Week 6.
- EASI75 at each scheduled assessment until Week 6.
- Change in SCORAD from baseline to each scheduled assessment until Week 6.
- Change from baseline to each week through Week 1 to 7 in ADSD (weekly average for each individual symptom).
 - Reduction of worst pruritus (one of the symptoms captured in the ADSD) (weekly average) of ≥ 4 points from baseline to each week through Week 1 to 7 among subjects with baseline worst pruritus (weekly average) of ≥ 4 .
- Change from baseline to each week through Week 1 to 7 in Eczema-related Sleep NRS (weekly average).
- Change in DLQI score from baseline to each scheduled assessment until Week 6.
- Reduction in DLQI of ≥ 4 from baseline to each scheduled assessment until Week 6 among subjects with baseline DLQI ≥ 4 .

For the binary endpoints, the same Cochran-Mantel-Haenszel test as for the Week 8 assessment will be applied. For the continuous endpoints, the repeated measurements model already described previously for the Week 8 assessments facilitates that the p-values, treatment differences, and 95% CIs can be derived for each visit up to Week 6 (or Week 7 for the change in ADSD (weekly average for each individual symptom) and Eczema-related Sleep NRS [weekly average]).

14.3.8 Analysis of pharmacodynamics and pharmacogenomics

Exploratory analyses of biomarkers will be performed for the total population as well as by disease severity.

A summary of the results will be included in the CTR if it is available in time for this. The full set of biomarker results will be reported in an addendum report to the CTR.

14.3.9 Analysis of safety

The analysis of safety will be based on the safety analysis set.

14.3.9.1 Adverse events

AEs will be coded during the course of the trial according to MedDRA. AEs will be presented by preferred terms and primary SOC.

Treatment-emergent AEs will be summarised; however, all AEs recorded during the course of the trial will be included in subject data listings. An event will be considered treatment-emergent if started after the first use of IMP or if started before the first use of IMP and worsened in severity after first dose of IMP. The tabulations described in the following will only include the treatment-emergent events. In each of the tabulations, AEs are defined by MedDRA preferred terms within primary SOC.

An overall summary of the number of events and the number (percentage) of subjects with any treatment-emergent AEs, deaths, SAEs, premature discontinuations from the trial due to AEs, treatment-related AEs and severe AEs will be presented.

The number of AEs and number of subjects with each type of AEs will be tabulated by treatment group.

The severity for each type of AE will be tabulated by treatment group. Where there are several recordings of severity for a given type of AE, severity will be taken as the most severe recording for that AE.

The causal relationship to IMP for each type of AE will be tabulated by treatment group. Where there are several recordings of causal relationship to the IMP for a given type of AE, causal relationship will be taken as the most-related recording from the last report of that AE, since that is when the investigator will be in possession of most information and therefore be best able to judge causal relationship.

Related AEs are defined as AEs for which the investigator has not described the causal relationship to IMP as 'not related'. The number of subjects with each type of related AE will be tabulated.

SAEs will be evaluated separately and a narrative for each will be given.

Adverse events of special interest will be tabulated by treatment group and listed.

AEs leading to withdrawal from trial and AEs leading to permanent discontinuation of IMP will be tabulated by treatment group and listed.

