Appendix 2: Classification of adverse events

Severity

The *severity* of the AE should be described in terms of mild, moderate or severe according to the investigator's clinical judgement.

Mild	An AE that is usually transient and may require only minimal treatment or therapeutic intervention. The event does not generally interfere with usual activities of daily living.
Moderate	An AE that is usually alleviated with additional specific therapeutic intervention. The event interferes with usual activities of daily living, causing discomfort but poses no significant or permanent risk of harm to the subject.
Severe	An AE that interrupts usual activities of daily living, or significantly affects clinical status, or may require intensive therapeutic intervention.

If the severity of an AE worsens, a new AE should be recorded.

Causality

The *causal relation* of the AE to the use of the IMP should be described in terms of probable, possible, or not related according to the investigator's clinical judgement. The categories are defined below.

Probably related	
Follows a reasonable temporal sequence from administration of the IMP.
 
Could not be reasonably explained by the subject's clinical state, environmental or toxic factors or other therapies administered to the subject.
 
Follows a known pattern of response to the IMP.
 
Disappears or decreases on cessation or reduction in dose of the IMP.
 
Reappears or worsens upon re-challenge.

------------------	---------------------------------------------------------------------------------------------------------------------------------------------------------------------------------------------------------------------------------------------------------------------------------------------------------------------------------------------------------------------------------------------------------------------------

Possibly related	
Follows a reasonable temporal sequence from the administration of the IMP.
 
Could also be reasonably explained by the subject's clinical state, environmental or toxic factors or other therapies administered to the subject.
 
Follows a known pattern of response to the IMP.

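### Read literally, the causality table in section 14.3.9.1 lets a later unrelated episode replace an earlier related episode of the same preferred term in the same subject

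*Combined protocol and SAP*

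**What the plan says.** All the main provisions are in section 14.3.9.1 of the combined protocol and SAP.

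- **Unit of tabulation.** "In each of the tabulations, AEs are defined by MedDRA preferred terms within primary SOC".
- **When the causality rule applies.** "Where there are several recordings of causal relationship to the IMP for a given type of AE".
- **The rule.** "causal relationship will be taken as the most-related recording from the last report of that AE".
- **The reason given.** "since that is when the investigator will be in possession of most information and therefore be best able to judge causal relationship".
- **The parallel rule for severity, one paragraph earlier.** "severity will be taken as the most severe recording for that AE".
- **Related AEs.** These have their own definition: any AE that the investigator has not rated as unrelated to IMP. They also have their own table of subjects by type of related AE. The text does not say whether the last-report rule feeds that table.

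Two other sections bear on how many records a subject can have under one term. Section 13.3 gives each AE its own start date, stop date and causality classification, so separate episodes are separate records. Appendix 2 adds: "If the severity of an AE worsens, a new AE should be recorded".

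**The concern.** The rule is triggered by several ratings within a type of AE, and a type of AE is a preferred term. The ratings it collapses can therefore come from separate episodes as well as from successive updates of one event. Having most information at the last report is a good reason to prefer an investigator's latest opinion of one event. It is no reason to let a second episode, weeks later, settle the causality of a first one that had already resolved.

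The plan treats the same situation differently for severity, where the worst recording stands, and it does not explain why causality should follow recency instead.

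Comparing safety with vehicle is a stated objective (Panel 3), and readers will use the by-term causality table to see which terms investigators attributed to the cream. Under the literal rule, a term that was once attributed to IMP in a subject can appear there as unrelated.

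**Working it through.** The plan gives no figure to reproduce here. The check is a comparison of readings, followed by a count of which way the two conventions can differ.

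**Step 1: one subject under each reading.** Take a hypothetical subject with two separate episodes of one preferred term, the first rated probably related and the second not related.

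| Rule | Entry for this subject and term |
|---|---|
| Literal: only the last report of the term counts | not related |
| Alternative: last report of each record, then most related across records | probably related |
| Related-AE table, definition applied record by record | counted as related |
| Related-AE table, if fed by the literal rule | not counted |

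If the literal rule drives the causality table and the record-by-record definition drives the related-AE table, the two outputs disagree for this subject. If the literal rule drives both, the subject is missing as a related case from both.

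**Step 2: direction.** Appendix 2 has three causality levels (not related, possibly, probably). With k records of a term there are 3^k possible sequences of ratings. Compare the last rating with the highest rating in the sequence.

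- Related becomes not related when the last rating is not related and at least one earlier rating is not: 3^(k−1) − 1 sequences. For k = 2 this is 3 − 1 = 2 of 9. For k = 3 it is 9 − 1 = 8 of 27.
- Probably becomes possibly when the last rating is possibly and at least one earlier rating is probably: 3^(k−1) − 2^(k−1) sequences. For k = 2 this is 3 − 2 = 1. For k = 3 it is 9 − 4 = 5.
- Lower category in total: 2 + 1 = 3 of 9 for k = 2, and 8 + 5 = 13 of 27 for k = 3. Higher category: 0 in both cases.

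These are counts of possible sequences, not probabilities. The zeros follow from comparing anything with a maximum. The count shows only that, against the worst-case convention used for severity, the literal rule can lower a classification and can never raise one.

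**Step 3: size.** Among subjects with two records of a term, the share of those with any related record who are tabulated as unrelated is

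P(first related and last not related) / P(at least one related).

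This is 0 if the two ratings always agree, and 1 if a related first record is always followed by an unrelated one and an unrelated first record is never followed by a related one. The documents give no information that narrows this range. They also give no proportion of subjects with repeat records, by which the share would have to be multiplied. No estimate for the trial is possible.

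**Step 4: the proposed rule and the related-AE definition.** If a subject's entry is the most-related rating across records, it is something other than not related exactly when at least one record is. That is the same set of subjects as the related-AE definition applied record by record, so the two tables then agree.

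**The case against.** The strongest reply is that the rule already means the right thing. If only the last record of a term counted, there would usually be one rating left, and the instruction to take the most related would have little to choose from. Those words do more work if one takes the last report of each event and then the most related across events. That reading also fits the stated reason. It is a fair reading and may be what the sponsor intended. But the trigger is the type of AE, the section defines that by preferred term, and a programmer could reasonably implement the literal version.

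Other parts of the reply also stand:

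- A record opened because an AE worsened continues the same event, so the later rating may well be the better informed. Appendix 2 shows that several records per term are to be expected, not that they are independent episodes.
- Section 11.4.5 keeps stinging and burning out of AE reporting unless serious. They are scored on their own scale and summarised under section 14.3.9.4. Part of the recurrent local reactions is therefore captured outside this table.
- The safety endpoint in Panel 3 is the number of AEs, which no causality rule alters.
- Section 14.3.12 has the SAP finalised before the code is broken, which is a natural place for this detail. That is a reason to settle the rule there, not to leave it open.

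A reader might infer that related events are under-counted throughout the safety outputs. The documents do not support that. The overall summary and the related-AE table are not stated to use the collapsing rule, all AEs are listed, and each SAE has a narrative. A reader might also infer that later records fall mostly after IMP has stopped and are then rated unrelated, or that a particular fraction of related cases is lost. Nothing in the documents shows where repeat records fall or how they are rated, and any such fraction would rest on assumed ratings.

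**Conclusion.** The point holds in a limited form. As written, the rule for the by-preferred-term causality table allows a later, separate episode to replace an earlier related one in the same subject. The reason given for the rule does not cover that case, and the adjacent severity rule handles it the other way. Relative to the severity convention, the literal rule can only lower a subject's classification.

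The effect is limited to subjects with two or more records of one term, in one descriptive table, and its size is unknown. Whether it differs between arms is also unknown; that would require related episodes followed by less-related ones to be more common in some arms than in others. The conclusion assumes the literal reading. If the sponsor meant the alternative reading, the only defect is that the text does not say so. Either way, the relation between this table and the related-AE table needs to be stated.

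**What to change.** In section 14.3.9.1 or the SAP, before unblinding, replace the causality rule with two steps and a link:

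1. Within each AE record, use the investigator's latest causality assessment.
2. Across a subject's records of the same preferred term, take the most-related of these, as is done for severity.
3. State that the same rule feeds the table of subjects with related AEs.

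Step 1 keeps the sponsor's reason where it applies: an investigator who changes opinion about an event can revise that record, and the revised rating is the one used.

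The cost is about one sentence and a small programming change. The downside is that related-AE counts may look slightly less favourable. For an AE re-entered because it worsened, an earlier related rating will also stand unless the investigator updates that record.

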14.3.9.2 Vital signs

The change in vital signs (blood pressure, pulse, body temperature) from baseline to each visit will be summarised as mean, standard deviation, median, minimum, and maximum values for each treatment group.

14.3.9.3 Clinical laboratory evaluation

The change in each of the laboratory parameters from baseline to each visit will be summarised by visit and treatment group as mean, standard deviation, median, minimum, and maximum values.

Laboratory parameters will be classified as 'low', 'normal' or 'high', depending on whether the value is below, within or above the reference range, respectively. A shift table will be produced showing the categories at baseline against those at end of treatment. Subjects with laboratory parameters outside the reference range will be listed.

14.3.9.4 Subject assessment of local tolerability

Subject assessment of local tolerability will be summarised by visit and treatment group.

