eDiary completion: ADSD and Eczema-related Sleep NRS ^m	Daily											11.7.1.1, 11.7.1.2
Subject assessment of efficacy and health-related quality of life – during trial visits												
POEM	X	X		X	X	X	X	X				11.7.1.3
DLQI	X	X		X	X	X	X	X				11.7.1.4
PGI-S	X	X		X	X	X	X	X				11.7.1.5
PGI-C					X	X		X				11.7.1.6
SF-36	X	X		X	X	X	X	X				11.7.1.7
EQ-5D-5L	X	X		X	X	X	X	X				11.7.1.8

	Screening ^a	Treatment period						End of treatment/early termination	Follow-up ^e	Primary endpoint visit at Week 8, if applicable ^f	Unscheduled visit, if applicable ^g	References (protocol sections)
		2	3 ^c	4	5	6	7					
Visit	1	2	3 ^c	4	5	6	7	8 ^d	9			
Week	-4 to -2	0		1	2	4	6	8	10			
Day	-28 to -14	1	4	8	15	29	43	57	71			
Visit window (days) ^b	-	-	±1	±3	±3	±3	±3	±3	±3			
WLQ ^a	X	X				X		X				11.7.1.9
TSQM						X		X				11.7.1.10
Investigator assessment of efficacy												
EASI	X	X		X	X	X	X	X		X		11.3.1
vIGA-AD	X	X		X	X	X	X	X		X		11.3.2
SCORAD	X	X		X	X	X	X	X		X		11.3.3
Investigator assessment of safety												
Vital signs	X	X		X	X	X	X	X			(X)	11.4.1
Physical examination	X	X						X			(X)	11.4.2
ECG	X	X						X			(X)	11.4.3
Chemistry, haematology ^o	X	X			X	X		X			(X)	11.4.4
Serology, total IgE, tuberculosis test ^p	X											11.4.4
Serum pregnancy test ^q	X										(X)	11.4.4
Urine pregnancy test ^q		X				X		X			(X)	11.4.4
	Screening^a	Treatment period										

								End of treatment/early termination	Follow-up ^e	Primary endpoint visit at Week 8, if applicable ^f	Unscheduled visit, if applicable ^g	References (protocol sections)
Visit	1	2	3 ^c	4	5	6	7	8 ^d	9			
Week	-4 to -2	0		1	2	4	6	8	10			
Day	-28 to -14	1	4	8	15	29	43	57	71			
Visit window (days) ^b	-	-	±1	±3	±3	±3	±3	±3	±3			
Urinalysis - dipstick	X	X				X					(X)	11.4.4
AEs/SAEs	X	X	X ^r	X	X	X	X	X	X	X	X	13
Subject assessment of local tolerability			X	X	X	X	X	X			X	11.4.5
Other assessments												
PK blood sample				X ^s								11.5.1
Skin swabs/skin microbiome		X						X				11.6.2
Skin biopsy and photography (optional)		X ^t		X ^u				X ^{u,v}				11.6.3
Check skin biopsy wound healing/suture removal			X		X				X			11.6.3
New AD lesions			X	X	X	X	X	X		X	X	11.7.2
Return of eDiary								X				11.7.1
End of trial form ^w								X	X	X		10.3, 11.9

- a) All subjects must use an emollient twice daily (or more, as needed) for at least 14 days before randomisation; the background treatment should preferably be an additive free, basic bland emollient

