- b) If the date of a trial visit does not conform to the clinical trial protocol, subsequent visits should be planned to maintain the visit schedule relative to baseline/randomisation at Day 1

- c) A visit at the trial site is not required on Day 4, a member of trial site personnel will call the subjects
- d) End of treatment assessments will be conducted at Week 8. Early termination: subjects, who discontinue IMP treatment prior to Week 8 or withdraw from trial will be asked to return to the trial site for end of treatment assessments at an early termination visit as soon as possible after the last IMP application for completion of all trial procedures scheduled for the visit at Week 8 (except for the skin biopsy, if the subject has consented to have skin biopsies obtained), and they will also be asked to return to the trial site 2 weeks after the last IMP application for a follow-up visit and at Week 8 for a primary endpoint visit
- e) All subjects will be asked to return to the trial site approximately 2 weeks after the last IMP application for assessment of safety at a follow-up visit
- f) Subjects who discontinue IMP treatment prior to Week 8 will be asked to return to the trial site at Week 8 for a primary endpoint visit
- g) Unscheduled visits may occur if subjects need to make a visit in between the scheduled visit dates due to an AE, difficulty complying with the trial protocol requirements, or a significant change in their disease state
- h) The informed consent form(s) must be signed prior to performing any protocol related procedures, including but not limited to screening evaluations and alteration of ongoing treatments unless medically justified
- i) All returned IMP tubes will be weighed by the CMO
- j) Relevant prior/concomitant medication should be included from 6 months prior to Day 1 (baseline) until end of trial
- k) Relevant medical history must be recorded from the subject's birth. In case medical history is incomplete at screening visit, missing data will be retrieved at Day 1 (baseline)
- l) BSA is assessed as a part of SCORAD
- m) Completion of the eDiary will be initiated at the latest 1 week prior to Day 1 (baseline). Compliance with the eDiary completion will be reviewed by the trial site staff throughout the trial.
- n) Only for subjects with a paid job.
- o) Subjects do not have to be fasting for safety laboratory samples

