11.4.5 Subject assessment of local tolerability

Subjects will provide an assessment of local tolerability according to the schedule of trial procedures (Section 4).

The subject will retrospectively be asked by the investigator to assess stinging/burning in connection with the IMP applications since their last visit. The highest (worst) skin reaction score across treatment area(s) will be recorded in the eCRF by use of the 4-point scale shown in Panel 12.

Panel 12: Subject assessment of local tolerability after IMP application

Grade	Stinging/burning
0 (none)	No stinging or burning
1 (mild)	Slight warm, tingling sensation, not really bothersome
2 (moderate)	Definitive warm, tingling sensation, that is somewhat bothersome
3 (severe)	Hot, tingling/stinging sensation that has caused definite discomfort

Subject assessment of local tolerability will be performed after safety assessments by the investigator (Panel 6). Local tolerability reactions are not reported as AEs; however, if they qualify as an SAE, they will be reported as described in Section 13.4.1.

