14.3.12 General principles

Unless otherwise stated, all significance tests will be 2-sided using the 5% significance level. All CIs will be presented with 95% degree of confidence.

An observed-cases approach will be used for tabulations of data by visit (i.e. involving only those subjects who attended each specific visit).

Categorical data will be summarised using the number and percentage of subjects in each category and treatment group. Continuous data will be summarised using the mean, median, standard deviation, minimum, and maximum values.

All the analyses specified in the protocol will be reviewed in relation to the blinded data actually obtained and the statistical analysis plan will be finalised before breaking the randomisation code.

Any changes from the statistical analysis planned in this clinical trial protocol will be described and justified in a protocol amendment, the statistical analysis plan and/or in the CTR dependent on the type of deviation.

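### Stinging/burning is summarised only visit by visit: the plan gives no count per strength of subjects ever affected or of their worst grade, and no stated place for unscheduled-visit scores

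*Combined protocol and SAP*

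**What the plan says.** Section 11.4.5 has the subject "assess stinging/burning in connection with the IMP applications since their last visit", on a 4-point scale from none to severe. Of the score itself it says: "The highest (worst) skin reaction score across treatment area(s) will be recorded in the eCRF". The same section keeps these reactions out of routine adverse event reporting: "Local tolerability reactions are not reported as AEs; however, if they qualify as an SAE, they will be reported as described in Section 13.4.1".

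Panel 2 (Section 4) marks the assessment at Day 4, at Weeks 1, 2, 4 and 6, in the shared Week 8 end-of-treatment/early-termination column, and at unscheduled visits. It is not marked at follow-up or at the primary endpoint visit. Footnote g of Panel 2 says: "Unscheduled visits may occur if subjects need to make a visit in between the scheduled visit dates due to an AE". The footnote goes on to name two further reasons, difficulty complying with the protocol and a significant change in disease state. Footnote d has subjects who stop early complete the Week 8 procedures (biopsy excepted) as soon as possible after their last application.

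The whole analysis plan for these data is one sentence in Section 14.3.9.4: "Subject assessment of local tolerability will be summarised by visit and treatment group". Section 14.3.12 adds: "An observed-cases approach will be used for tabulations of data by visit". It also has categorical data shown as number and percentage of subjects per category and treatment group.

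**The concern.** Comparing the safety of the four strengths with vehicle is a stated objective (Panel 3). Section 5.3 describes this as the first trial of the cream in atopic dermatitis and says its results will support dose selection for phase 3. A natural tolerability question is how many subjects on each strength had stinging or burning at any time, and how bad it was at its worst. A set of by-visit rows cannot answer that, because it does not show whether the same or different subjects make up each row.

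Two collection features add to the problem. Unscheduled-visit scores are collected but have no stated place in the table. Early-termination scores may be mixed with true Week 8 scores.

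**Working it through.** The plan states no figure on this point, so there is none to reproduce. The check has three parts: what the by-visit table can identify, where each kind of score goes, and whether another output fills the gap.

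**1. From by-visit rates to subjects ever affected**

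Inputs:
- six scheduled assessments: Day 4 and Weeks 1, 2, 4, 6 and 8 (Panel 2);
- 50 subjects per arm (Section 7.2);
- assumed: a reaction rate p that is equal at all six assessments, with every subject assessed each time.

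Formulas for the share of subjects ever affected:
- minimum (the same subjects at every visit): p;
- independent visits: 1 − (1 − p)^6;
- maximum (different subjects at every visit): 6p, capped at 1.

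| Assumed p | Minimum | Independent | Maximum | Subjects of 50 (minimum / independent / maximum) |
|---|---|---|---|---|
| 2% | 2% | 1 − 0.98^6 = 11.4% | 12% | 1 / 5.7 / 6 |
| 5% | 5% | 1 − 0.95^6 = 26.5% | 30% | 2.5 / 13.2 / 15 |
| 10% | 10% | 1 − 0.90^6 = 46.9% | 60% | 5 / 23.4 / 30 |

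Two arms could therefore show the same 10% in all six rows while one had 5 subjects ever affected and the other 30.

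**2. Where each score goes**

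- *Scheduled visit.* The score enters its row, among those who attended.
- *Unscheduled visit.* No rule places it. Suppose, for illustration, that a subject attends on Day 20, between Week 2 (Day 15) and Week 4 (Day 29). If the Day 20 visit then counts as the last visit, the Week 4 score covers only the time after Day 20. A reaction confined to Days 15 to 20 is recorded at the unscheduled visit and may appear in no scheduled row. A reaction that persists would still show at Week 4.
- *Early termination.* Suppose a subject stops on Day 10. The score describes the days since the Week 1 visit but is collected in the column used for Day 57. The plan does not say whether it is shown as Week 8, as the nearest visit, or separately.

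**3. Whether another output fills the gap**

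Section 14.3.9.1 counts subjects with each type of AE and takes the most severe recording for that type. That is the per-subject, worst-grade form wanted here. Section 11.4.5 excludes non-serious local reactions from it. Section 14.3.9.4 specifies no across-visit summary and no listing.

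**The case against.** The strongest reply is that the planned table is more informative than it first looks. Sections 14.3.9.4 and 14.3.12 together give the number and percentage of subjects at each grade, per strength, at every visit. Early-termination scores do have a scheduled column. By-visit display is also the plan's format for changes in vital signs and laboratory values. Local tolerability is not a listed endpoint; the safety endpoint in Panel 3 is the number of AEs. Extra tables and visit-assignment rules can go into the statistical analysis plan, which Section 14.3.12 says will be finalised before the code is broken.

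Most of this stands, and it limits the point. A reader might infer that no table shows subjects per strength with a reaction. That is wrong: each visit row shows them, and only the count across the treatment period is missing. A reader might also infer that the worst reactions come to light at unscheduled visits. The documents do not say so. Footnote g gives three reasons for such visits, and a non-serious local reaction is not itself an AE under Section 11.4.5.

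A third tempting inference is that subjects with reactions leave, so that the table as a whole understates differences between strengths. That would need an assumed link between reactions and stopping. Even then, the loss would fall on the rows between stopping and Week 8. Reactions before stopping can appear in earlier rows, and the early-termination score can re-enter through the shared column. Reasons for discontinuation are also presented by treatment group (14.3.1).

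What the reply does not supply is the missing count. The protocol names by-visit display as the method for these data, and no separate analysis-plan text in the documents adds to it.

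**Conclusion.** The point holds as a limited but real gap. No planned output gives, per strength, the number of subjects who ever had stinging or burning during treatment, or their worst grade, and the AE tables cannot supply it. Handling of unscheduled scores is unstated, so a reaction recorded there may be missing from every scheduled row. That is a possibility left open by silence; the plan does not say such scores are discarded. Early-termination scores may be mixed with true Week 8 scores.

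The size can only be illustrated. At an assumed constant 10% per scheduled assessment with complete attendance, the share ever affected could lie anywhere from 10% to 60% (5 to 30 of 50), with 47% under independence. The documents give no reaction rate, so these figures show how little the by-visit rows identify; they do not forecast the result. The direction of any distortion between strengths is not established. The efficacy analyses and the sample size are unaffected. The change should be made because it is cheap and bears on a stated safety objective.

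**What to change.** In Section 14.3.9.4, add a table of each subject's worst post-baseline grade (none, mild, moderate, severe) as number and percentage by treatment group. Use the safety analysis set as denominator, and take the worst over all scheduled, unscheduled and early-termination assessments. Show subjects with no post-baseline score as a separate line. Keep the by-visit table, and state that early-termination scores are assigned by actual trial day so that they are not read as Week 8 scores.

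The cost is one extra table and a short assignment rule, using data already collected. One drawback should be noted beside the table: subjects with more assessments have slightly more chance of a high worst grade. The by-visit table, kept as support, helps the reader judge that.
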